3.1 Population (base)

The study population will be selected from the outpatient clinical from hospitals based in the Netherlands (Groningen, Almelo, Amsterdam), Canada, (Toronto, Calgary, Vancouver) and Malaysia (Kuala Lumpur).

3.2 Inclusion criteria

- Age ≥ 18 and ≤ 75 years
- Urinary protein excretion > 500 mg/24hr and ≤ 3500 mg/24hr in a 24-hr urine collection
- eGFR ≥ 25 mL/min/1.73m²
- On a stable dose of an ACEi or ARB for at least 4 weeks prior to randomization
- Willing to sign informed consent
- Women of Child-Bearing Potential (WOCBP):
 - WOCBP must be using an acceptable method of contraception to avoid pregnancy throughout the study and for up to 4 weeks after the last dose of study drug in such a manner that the risk of pregnancy is minimized.

- WOCBP must have a negative serum or urine pregnancy test result (minimum sensitivity 25 IU/L or equivalent units of HCG) within 0 to 72 hours before the first dose of study drug.
- Women must not be breast-feeding.

WOCBP **comprises** women who have experienced menarche and who have not undergone successful surgical sterilization (hysterectomy, bilateral tubal ligation, or bilateral oophorectomy) or who are not post-menopausal.

3.3 Exclusion criteria

- Diagnosis of type 1 or type 2 diabetes mellitus
- Urinary protein excretion > 3500 mg/day
- Peripheral Vascular Disease
- Autosomal dominant polycystic kidney disease or autosomal recessive polycystic kidney disease, lupus nephritis, or ANCA-associated vasculitis
- Indication for immunosuppressants as per the treating physician's judgment.
- Receiving cytotoxic therapy, immunosuppressive therapy, or other immunotherapy for primary or secondary renal disease within 6 months prior to enrolment.
- Active malignancy aside from treated squamous cell or basal cell carcinoma of the skin.
- Use of the co-interventional treatments (outlined in section 4.2) within 6 weeks of screening will not be allowed.
- Any medication, surgical or medical condition which might significantly alter the absorption, distribution, metabolism, or excretion of medications including, but not limited to any of the following:
 - History of active inflammatory bowel disease within the last six months;
 - Major gastrointestinal tract surgery such as gastrectomy, gastroenterostomy, or bowel resection;
 - Gastro-intestinal ulcers and/or gastrointestinal or rectal bleeding within last six months;
 - Pancreatic injury or pancreatitis within the last six months;
 - Evidence of hepatic disease as determined by any one of the following: ALT or AST values exceeding 3x ULN at the screening visit, a history of hepatic encephalopathy, a history of esophageal varices, or a history of portocaval shunt;
 - Evidence of urinary obstruction or difficulty in voiding at screening
- History of severe hypersensitivity or contraindications to dapagliflozin

- History of hypersensitivity or contraindications to iodinated contrast media
- Subject who, in the assessment of the investigator, may be at risk for dehydration or volume depletion that may affect the interpretation of efficacy or safety data
- Participation in any clinical investigation within 3 months prior to initial dosing.
- Donation or loss of 400 ml or more of blood within 8 weeks prior to initial dosing.
- History of drug or alcohol abuse within the 12 months prior to dosing, or evidence of such abuse as indicated by the laboratory assays conducted during the screening.
- History of noncompliance to medical regimens or unwillingness to comply with the study protocol.
- Any surgical or medical condition, which in the opinion of the investigator, may place the patient at higher risk from his/her participation in the study, or is likely to prevent the patient from complying with the requirements of the study or completing the study.
- Pregnancy or breastfeeding
- WOCBP who are unwilling or unable to use an acceptable method to avoid pregnancy for the entire study period and up to 4 weeks after the last dose of study drug.

Any disqualifying proteinuria or eGFR level may be repeated one time, at the discretion of the investigator and where there is a clinical reason to do so. The repeat value should be assessed prior to the subject recorded as having screen failed. If the repeat value falls within the ranges defined by the protocol and the patient meets all other inclusion criteria, the patient is eligible for the study.

3.4 Sample size calculation

With a sample size of 50 patients completing the study and assuming a conservative standard deviation of 0.7 in log transformed proteinuria (within-subject standard deviation of 0.475), the trial will have 80% power to detect a mean reduction in albuminuria of 25% (i.e, $\delta=0.288$ on the log-transformed proteinuria scale) or more with dapagliflozin compared to placebo (alpha 0.05). This calculation is based on individual patient data from various clinical trials on the anti-proteinuric effects of different agents in diabetes and non-diabetes trials for which we have the individual patient data including ROAD, RENAAL and IDNT trials. For calculation of the sample size, the percent change in proteinuria is log-transformed to take into account the skewed distribution of proteinuria. Under the assumption that no carry-over effects and no period effects occur, a paired-t-

test is deemed appropriate to calculate the sample size. Using these assumptions, we calculate that 50 patients completing the study will provide 80% power to detect a 25% reduction in albuminuria. Assuming that approximately 5% of patients will discontinue the study prematurely, we intend to enrol 53 subjects.

We believe a reduction of >25% with dapagliflozin versus placebo can be detected. We recently published a large analysis of patients with diabetes and demonstrated that dapagliflozin decreased proteinuria by 33%. Trials with other SGLT2 inhibitors have also documented proteinuria reductions of approximately 30%.

4. TREATMENT OF SUBJECTS

4.1 Investigational product/treatment

Dapagliflozin and matching placebo tablets will be provided by Astra Zeneca. Patients will take 10 mg dapagliflozin (once daily) or matching placebo according to randomised treatment scheme.

The marketed 10 mg dose has been demonstrated to be well tolerated and effective for the treatment of type 2 diabetes and post-hoc analyses in patients with CKD and proteinuria have shown that this dose is effective in reducing renal risk markers (i.e. blood pressure, proteinuria) independent of its glucose lowering effect⁸⁻¹⁰. In addition, in a dedicated CKD clinical trial this dose was found to be well tolerated⁹. From a pharmacokinetic and pharmacodynamic perspective dapagliflozin 10 mg is appropriate for use in patients with CKD.

Study medication is received at the study site by a designated person, handled and stored safely and properly, and kept in a secured location. The study medication will be stored according to the instructions specified on the drug labels. Storage conditions are adequately monitored. Subjects are asked to return all unused study drug and packaging at the end of the study or at the time of study drug discontinuation or in every visit to the outpatient clinic. Appropriate documentation of the subject specific dispensing process is maintained. Returned and unused drugs are destroyed by the local pharmacy department at the end of the study.

4.2 Use of co-intervention (if applicable)

Use of the following treatments will not be allowed from 6 weeks before the start of the study and during the study as these medications may interfere with the evaluation of safety, tolerability and/or efficacy.

- Aldosterone antagonists
- Direct renin inhibitors

Systemic corticosteroids and immunosuppressants

Patients who are receiving such medication(s) should be excluded, or if ethically justified, the medication(s) may be withdrawn according to the manufacturer's/investigator's instructions prior to start of the screening period. Withdrawal of medication is done after consultation with the patient and patients' physician.

The dose of diuretics and vitamin-D analogues should be stable at least 4 weeks prior to enrolment. Dose adjustments of diuretics or vitamin-D analogues are strongly discouraged during the trial.

In subjects receiving oral medications containing non-steroidal anti-inflammatory drugs (NSAIDs), ephedrine, phenylephrine, pseudoephedrine, or phenylpropanolamine, administration of such medications is recommended to be discontinued at least 48 hours before iohexol injection and should not be resumed until completion of the GFR measurement procedure. Continuous NSAID use is not permitted during the study. NSAIDs use for several days for pain management is permitted as long as it is not during the days prior to GFR / proteinuria assessments.

Drugs which lower seizure threshold, especially phenothiazide derivatives including those used for their antihistaminic properties, are not recommended for use with iohexol.

Others include monoamine oxidase (MAO) inhibitors, tricyclic antidepressants, CNS stimulants, psychoactive drugs described as analeptics, major tranquilizers, or antipsychotic drugs. The dose of such medications, if applicable, are recommended to be discontinued at least 48 hours before iohexol injection and should not be resumed for at least 24 hours following iohexol injection.

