b Total 24-hr urinary dapagliflozin excretion will also be measured at the end of each treatment period

c WOCBP must have a negative serum or urine pregnancy test result (minimum sensitivity 25 IU/L or equivalent units of HCG) within 0 to 72 hours before the first dose of study drug.

d Subject will be asked to collect 24 hour urine after informed consent is obtained. The subject will be requested to return the urine sample to the site on the following day.

e Specify details about specimen collection will be provided in the laboratory manual. Table 1-2 will list the laboratory assessment to be performed.

f Specify details about specimen collection, storage and processing will be provided in the laboratory manual.

g Visit 6 Serum or Urine Pregnancy Test is required for Canada sites per local regulatory requirement

Study Periods and Procedures:

Screening

Chronic Kidney Disease aged between 18 and 75 years, proteinuria levels between 500 and 3500 mg/24-hour, and an eGFR ≥ 25 ml/min/1.73m² who are on an ACEi or ARB, or can start with an ACEi or ARB, will be eligible for protocol-specific assessment during the screening period. Signature of the protocol-specific informed consent form constitutes the first procedure of the screening period, followed by the assignment of a unique subject number. Protocol-specific assessments and procedures may then be performed, as part of the screening visit, to evaluate the subject's eligibility. During the screening period, subjects will maintain their stable doses of commercially available ACEis or ARBs, and diuretic medication.

When all inclusion and exclusion criteria have been evaluated and the requirements for entry into the study have been met, the entry into run-in period or double blind treatment period will be scheduled. If the patient does not qualify based on the laboratory data, the patient is allowed to be re-screened within 3 weeks of the original screening date. The laboratory data based on which the patient failed should be repeated.

Run-in Period:

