8.3 Recording of Adverse Events

- *Time Period for Collection of Adverse Events*

For this study, SAEs, discontinuations due to AEs (DAEs), and AEs of special interest will be collected from the time of signing the informed consent and throughout the study, including the run-in and wash-out periods. Information about all adverse events (serious or not) will be recorded in source documents (eg, progress notes) according to good clinical practice, and retained at the investigative sites.

- *Follow-up of Unresolved Adverse Events*

Any SAEs, DAEs, or AE of special interest will be followed by the investigator until resolution or until a clinically stable outcome is reached, or until further follow-up is no longer considered by the investigator to provide clinically meaningful information.

- *Variables*

The following variables will be collected for each SAE/DAE/AE of special interest: AE (verbatim).

The date and time when the AE started and stopped.

Intensity.

Whether the AE is serious or not.

Investigator causality rating against the study drug (yes or no).

Action taken with regard to study drug.

AE caused patient's withdrawal from study (yes or no).

Outcome.

In addition, the following variables will be collected for SAEs:

Date AE met criteria for a serious AE.

Date Investigator became aware of the SAE.

AE is serious due to.

- a. Date of hospitalisation (if applicable).
- b. Date of discharge (if applicable).
- c. Probable cause of death (if applicable).

- d. Date of death (if applicable).
- e. Autopsy performed (if applicable).
- f. Causality assessment in relation to Study procedure(s).
- g. Causality assessment in relation to other medication (e.g., concomitant medication, background therapy).

Description of intensity.

The intensity of the reported SAEs/DAEs/AE of interest will be assessed according to the following scale:

- Mild (awareness of sign or symptom, but easily tolerated).
- Moderate (discomfort sufficient to cause interference with normal activities).
- Severe (incapacitating, with inability to perform normal activities).

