8.4 Serious Adverse Event Collecting and Reporting

Following the subject's written consent to participate in the study, all SAEs, whether related or not related to study drug, must be collected, including those thought to be associated with protocol-specified procedures. All SAEs will be collected that occur during the screening period and within 30 days of discontinuing dosing. If applicable, SAEs must be collected that relate to any later protocol-specific procedure (such as follow-up skin biopsy).

The investigator should report any SAE occurring after these time periods that is believed to be related to study drug or protocol-specified procedure.

An SAE report should be completed for any event where doubt exists regarding its status of seriousness.

If the investigator believes that an SAE is not related to study drug, but is potentially related to the conditions of the study (such as withdrawal of previous therapy, or a complication of a study procedure), the relationship should be specified in the narrative section of the SAE Report Form.

SAEs that result in death or are life threatening should be reported expedited to the competent authorities. The expedited reporting will occur not later than 7 days after the responsible investigator has first knowledge of the adverse reaction. This is for a preliminary report with another 8 days for completion of the report. Concurrently, the sponsor's principal investigator and project leader will report SAEs accompanied by a cover page mentioning the study code, patient number, country, investigator, seriousness to AstraZeneca via the e-mail box [contact] within the same timelines.

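### Section 4.2 places medication withdrawal for trial entry at least 6 weeks before signed consent and before adverse event collection, against the protocol's own consent rule

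*Protocol*

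**What the plan says.** Protocol section 4.2 lists aldosterone antagonists, direct renin inhibitors, systemic corticosteroids and immunosuppressants, and states: "Use of the following treatments will not be allowed from 6 weeks before the start of the study and during the study". The reason given is the trial's own: "as these medications may interfere with the evaluation of safety, tolerability and/or efficacy". Exclusion is the default for patients taking these drugs. The alternative is "or if ethically justified, the medication(s) may be withdrawn according to the" manufacturer's or investigator's "instructions prior to start of the screening period. Withdrawal of medication is done after consultation with the patient" and the patient's physician.

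Four other places fix the timing:

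- Section 3.3 says that use of the section 4.2 treatments "within 6 weeks of screening will not be allowed".
- Section 3, under Screening, says that signing the trial's "informed consent form constitutes the first procedure of the screening period".
- Footnote a of the Time and Events Table requires consent before any study-specific procedure, and section 5.4 requires it before any study-specific activity.
- Section 8.3 says that SAEs, discontinuations due to adverse events and adverse events of special interest "will be collected from the time of signing the informed consent and throughout the study". Section 8.4 likewise ties SAE collection to written consent and extends it only forward in time.

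**The concern.** The withdrawal is made so that a patient can enter the trial, because the stated alternative is exclusion. It therefore belongs under the same consent and safety arrangements as any other trial-driven intervention, and the written order of events puts it outside both.

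The protocol treats its other trial-driven drug change differently. Starting or uptitrating an ACEi or ARB happens in the run-in, after screening and consent, and section 8.3 expressly includes the run-in in event collection. Only the section 4.2 withdrawal comes before either.

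The benefit and risk text does not fill the gap. Section 10.4 and the burden paragraph in the Summary discuss study visits, blood and urine sampling, GFR measurement and the study drug. Neither mentions stopping existing therapy.

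What is at stake is subject protection and the completeness of the safety record. Nothing here bears on the primary estimate, the power or the randomised comparison.

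**Working it through.** No statistical figure is in question. The check is to put the timing statements in order, taking the day consent is signed as day 0.

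1. **Consent.** It is the first procedure of screening (section 3), so screening starts on day 0.
2. **Withdrawal under section 4.2.** It takes place before the screening period starts, so before day 0.
3. **Drug-free interval under section 3.3.** There must be no use within 6 weeks of screening. 6 weeks × 7 days = 42 days, so the last intake is on day −42 or earlier.
4. **Event collection.** It opens at signature (sections 8.3 and 8.4), so on day 0.
5. **Gap.** 0 − (−42) = at least 42 days between last intake and both consent and event collection.

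For immunosuppressive therapy given for renal disease, section 3.3 separately requires at least 6 months before enrolment, so that interval is longer.

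**Does the other anchor remove the gap?** Section 4.2 counts its 6 weeks from the start of the study, which is not defined. Suppose this means randomisation.

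- The Summary gives a total duration of 25 weeks, or up to 41. The Time and Events Table runs 24 weeks from randomisation to the last visit. That leaves about 25 − 24 = 1 week before randomisation on the short route and up to 41 − 24 = 17 weeks with the longest run-in.
- On the short route, 6 weeks before randomisation is still about 6 − 1 = 5 weeks before consent.
- With a long run-in, 6 weeks before randomisation could fall after consent. Even then, the withdrawal sentence in section 4.2 and the criterion in section 3.3 are both tied to screening, so the order in steps 1 to 5 is unchanged.

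**What is recorded for harm from a withdrawal:**

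| When harm occurs | Record under the written rules |
|---|---|
| Arises and resolves before consent | No AE or SAE report. Section 3 asks for medical history in the eCRF at screening, including hospital admission in the last year, prior acute kidney injury and hypovolaemia, so some of it may appear there |
| Starts or persists after consent | Collected if it is an SAE, leads to discontinuation, interruption or dose reduction of study drug, or is an event of interest. Canadian sites record all AEs in the eCRF (section 8.2.2). Other non-serious events elsewhere go to source documents (section 8.3) |
| Patient never reaches consent | No trial record |

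**Consistency with the consent rule.** Footnote a and section 5.4 put consent first. A site cannot follow them and also withdraw a drug for trial entry before screening, unless stopping a drug for the trial does not count as a study-specific activity. The protocol does not say that.

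**The case against.** Several points on the other side stand.

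- **Safeguards exist.** Exclusion is the default, the alternative applies only if ethically justified, and both the patient and the patient's physician are consulted.
- **The route is narrower than the list of four drug classes suggests.** Section 3.3 already excludes patients with an indication for immunosuppressants, and those given immunosuppressive therapy for renal disease within 6 months of enrolment.
- **Use may be rare.** The documents give no count, and it could be zero.

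A reader might infer that such harm is never consented to and never reaches the database. The documents do not support that. Medical history at screening can record admissions, acute kidney injury and hypovolaemia from the gap, and qualifying harm present after consent is collected and followed. Section 10.2 describes an invitation letter that explains the study and 2 weeks to decide. The letter is not in the file and consent pages were removed from the review copy, so nothing can be said about what patients are told there.

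A reader might also see section 8.4 as a further contradiction, because it names "withdrawal of previous therapy, or a complication of a study procedure" as a condition of the study that may lie behind an SAE. That is only an example. It can refer to stops made after consent, such as the drugs that section 4.2 recommends pausing at least 48 hours before iohexol.

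Nor do the documents show that harm is most likely in these weeks.

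None of this removes the conflict of order. Consultation is not signed consent, and a medical history entry is not an AE or SAE report: section 8.3's intensity and causality assessments and its follow-up requirement apply only to events collected from consent.

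**Conclusion.** The point holds as a contradiction in timing. Section 4.2, read with sections 3, 3.3, 8.3 and 8.4, places a trial-driven withdrawal at least 42 days before signed consent and before AE/SAE collection, while footnote a and section 5.4 require consent first. Harm that arises and resolves in that gap goes unreported as an AE or SAE, and harm in a patient who never consents goes unrecorded by the trial.

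This rests on two readings: that screening in section 3.3 means the visit at which consent is signed, and that stopping a drug in order to enter the trial is a study-specific activity. The number of patients affected is unknown. The contradiction still merits correction, because it concerns the protection of participants and the remedy is cheap.

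**What to change.** Reconcile sections 3 (Screening, and footnote a of the Time and Events Table), 3.3, 4.2, 5.4, 8.3 and 8.4 so that signed consent and the start of AE/SAE collection precede any medication change made for the purpose of the trial. In the same revision, reconcile the two anchors for the 6-week interval, which is counted from the start of the study in section 4.2 and from screening in section 3.3. No view is taken on whether, when or how any drug should be withdrawn, or on the length of the interval.

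The cost is protocol wording, earlier consent for the few patients who would enter by this route, and slightly more pre-treatment events to record. Other patients are unaffected.

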5. INVESTIGATIONAL PRODUCT

5.1 Name and description of investigational product(s)

Drug name: dapagliflozin (Forxiga, AstraZeneca, RPF-EU-12-MB102-016); Chemical structure: (2S,3R,4R,5S,6R)-2-[4-chloro-3-(4-ethoxybenzyl)phenyl]-6-(hydroxymethyl)tetrahydro-2H-pyran-3,4,5-triol;

Product Description and Dosage Form	Dosage form and strength	Manufacturer
Dapagliflozin 10mg Tablet	10 mg Green, plain, diamond shaped, film coated tablet (orally)	Astra Zeneca
Placebo Matching Dapagliflozin Tablet	Green, plain, diamond shaped, film coated tablet. Does not contain active ingredient	Astra Zeneca

